6.7.1. Primary outcome

To evaluate whether electronic reporting of HAQ through a smartphone app is comparable to the

traditional touch screen solution in the rheumatology outpatient clinics among patients with inflam-

matory arthritis.

6.7.2. Secondary outcomes

To evaluate whether electronic reporting of VAS pain, VAS fatigue, VAS global assessment, PASS,

anchoring question, BASDAI and BASFI through a smartphone app is comparable to the traditional

touch screen solution in the rheumatology outpatient clinic among patients with inflammatory arthri-

tis. In addition, to evaluate whether electronic reporting of PROM through a smartphone app is com-

parable to the traditional touch screen solution in the rheumatology outpatient clinic stratifying by

diagnosis (RA, PsA or SpA). Additionally, to evaluate whether the participants prefer reporting

PROM electronically through the DANBIO app or the traditional touch screen solution in the rheu-

matology outpatient clinic.

6.8. Power and sample size considerations

In a two one-sided tests analysis for additive equivalence of paired means with bounds -0.11 and 0.11

for the mean difference in HAQ and a significance level of 0.05, assuming a mean difference of 0

HAQ points, a common standard deviation of 0.62 HAQ points and correlation 0.95 (between

measures), a sample size of 36 pairs (12 patients with each condition) is required to obtain a power

of at least 0.9. The actual power is 90.2%.

Minimal sample size: based on the same assumptions as above a sample size of 29 pairs (in total) is

required to obtain a power of at least 0.8 (80.7%).

It was decided by the steering committee for this study, that in order to at least attempt to explore

equivalence margins, within each disease group (i.e. RA, PsA and SpA) separately, a sample size of

20 pairs of each disease group would be feasible; i.e. enrolling 60 patients in total (corresponding to

a power of 99.2%).

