Data will be analysed using SAS Proc Mixed. The MIXED procedure fits a variety of mixed linear models. A mixed linear model is a generalization of the general linear model (GLM); the generalization being that the data are permitted to exhibit correlation (i.e., from two measures on the same participant). Having a continuous outcome as the dependent variable (e.g. HAQ), our modelling component of SAS PROC MIXED will include both fixed (period [I or II]; questionnaire [App or Touch]; rheumatic condition [RA or PsA or SpA]) and random participant (i: 1, 2, 3,, n = 60) effects. In case of missing data for some of the participants, PROC MIXED handles the missing values implicitly adjusting for the missing values; unlike a GLM approach a mixed linear model uses the data for the periods where there is data and ignores the periods for which there is no data (10). Provided the data are "missing at random", the estimates from PROC MIXED are valid (e.g., the missing data cannot caused by some event happening during the first questionnaire exercise) (11). Imputations will not be used to replace missing data in the primary analyses, but will potentially be included in a sensitivity analysis to assess the impact/robustness of the conclusions.

Statistical interpretation of agreement: According to Piaggio et al. (12), equivalence is declared if the entire 2-sided 95%CI is included within the equivalence margin. Therefore, in this study a 2-sided 95% CI for the paired difference in each individual PROM (e.g HAQ) will be derived from the mixed linear model and agreement will be declared if the 95% CI of difference between PROMs is within the prespecified equivalence range (e.g., -0.11 HAQ-points to +0.11 HAQ-points). These margins (Table 1) are based on half of the effect that is usually considered a clinically relevant reduction in the individual PROMs. Thus, based on a superiority approach it was decided *a priori* that a 95% CI

excluding differences between groups of greater than half the MID/MCID units would be interpreted

as indicating the absence of a clinically meaningful difference (agreement) (13). No interim analyses

will be performed. All reported P values will be two-sided, based on a superiority assumption, and

will not be adjusted for multiple comparisons.

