To evaluate whether electronic reporting of PROMs through a smartphone app is comparable to the standard touchscreen solution in the rheumatology outpatient clinic among patients with RA, PsA and axSpA in standard clinical care.

Hypothesis

Use of a smartphone app for registration of PROMs in rheumatology yields comparable results with the standard touchscreen solution in the outpatient clinic.

Objectives

Primary objective

To demonstrate a reasonably equivalent* self-reported disability status determined by the HAQ-DI score when using a smartphone app compared to the standard touchscreen solution among patients with inflammatory arthritis enrolled in a randomised, crossover, agreement study.

*Equivalence of HAQ-DI disability status will be concluded if the 95% confidence interval for monitoring difference is within ± 0.11 HAQ-DI score points.

Secondary objectives

To evaluate whether electronic reporting of VAS (Visual Analog Scale) pain, VAS fatigue, VAS global assessment, Patient Acceptable Symptom State (PASS), anchoring question, Bath Ankylosing Spondylitis Disease Activity Index (BASDAI) and Bath Ankylosing Spondylitis Functional Index (BASFI) through a smartphone app is reasonably comparable to the standard touchscreen solution in the rheumatology outpatient clinic among patients with inflammatory arthritis. In addition, to explore whether the electronic reporting of PROMs through a smartphone app is comparable to the standard touchscreen solution in the rheumatology outpatient clinic when stratifying by diagnosis (RA, PsA or axSpA). Additionally, to evaluate whether the participants prefer reporting PROMs electronically through the DANBIO app or the standard touchscreen solution in the rheumatology outpatient clinic.

Section 3: Study Methods

Trial design

The trial is a randomised, within-participant, crossover design including patients with RA, PsA and axSpA. In a crossover study, each participant acts as his/her own control for the questionnaire comparisons; thus, each patient answered the PROM questionnaires through the DANBIO app and the touchscreen in a randomised order at two consecutive time periods. The PROM questionnaires answered in the DANBIO app was exactly the same questionnaires as the participant answered on the touchscreen in the outpatient clinic.

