The sample size was based on the following assumptions: in a two one-sided tests analysis for additive equivalence of paired means with bounds -0.11 and 0.11 for the mean difference in HAQ-DI and a significance level of 0.05, assuming a mean difference of 0 HAQ-DI points, a common standard deviation of 0.62 HAQ-DI points (7) and correlation 0.95 (between measures), a sample size of 36 pairs (12 patients with each condition) were required to obtain a power of at least 90%.

Minimal sample size: based on the same assumptions as above a sample size of 29 pairs in total (10 patients with each condition) was required to obtain a power of at least 80%. It was decided by the steering committee for this study, that in order to at least attempt to explore equivalence margins within each disease group (i.e. RA, PsA and axSpA) separately, a sample size of 20 pairs of each disease group would be feasible; i.e. enrolling 60 patients in total (corresponding to a power of 99.2%).

Framework

Although the main objective is to explore similarity between PROM devises, the precision of the estimates will be derived from a superiority analysis framework. The objective of this crossover trial is to evaluate whether electronic reporting of HAQ-DI, VAS pain, VAS fatigue, VAS global assessment, PASS, anchoring question, BASDAI and BASFI through the DANBIO app is comparable to the standard touchscreen solution in the outpatient clinics among patients with inflammatory arthritis. Furthermore, to evaluate whether electronic reporting of PROMs through the DANBIO app is comparable to the standard touchscreen solution in the outpatient clinic stratifying by diagnosis (RA, PsA or axSpA). Thus, in the outcomes listed above we will test for equivalence.

Additionally, this study will evaluate whether the participants prefer reporting PROMs electronically through the DANBIO app or the standard touchscreen solution in the outpatient clinic. Hence, this outcome will be tested for superiority.

Statistical interim analyses and stopping guidance

No interim analyses were performed during this trial; no data analyses will be done before closure of the final SAP.

Timing of final analysis

Final analysis will be performed collectively as all outcomes are short-term outcomes.

Timing of outcome assessments

The timing of outcome assessments is illustrated below in Table 1:

Table 1: Overview of time points for PROM data registration in the DANBIO-App trial

ction	

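### The stated powers are for a 90% CI rule (TOST at 0.05), but equivalence is declared on the 95% CI, so every stated power is too high

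*Protocol*

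**What the plan says.** Protocol section 6.8 sets out the method: "In a two one-sided tests analysis for additive equivalence of paired means with bounds -0.11 and 0.11". It continues with the level and the assumed true difference, "for the mean difference in HAQ and a significance level of 0.05, assuming a mean difference of 0", and the variability, "HAQ points, a common standard deviation of 0.62 HAQ points and correlation 0.95 (between" measures). From these it concludes that "a sample size of 36 pairs (12 patients with each condition) is required to obtain a power" of at least 0.9, and adds "The actual power is 90.2" per cent. It then gives a minimal size of 29 pairs with 80.7% power. It explains the choice of 60 participants (20 per diagnosis) by the wish to look at each diagnosis separately, and attaches 99.2% power to that total.

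Protocol section 6.10 gives the decision rule: "equivalence is declared if the entire 2-sided 95%CI is included within the equivalence margin". It applies this rule to HAQ with the range −0.11 to +0.11.

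The SAP carries both sides forward. Section 2, Primary objective: "Equivalence of HAQ-DI disability status will be concluded if the 95% confidence interval for monitoring difference is within" ±0.11 points. Section 3, Power and sample size, keeps the calculation at 0.05: "a sample size of 36 pairs (12 patients with each condition) were required to obtain a power of at least 90" per cent.

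**The concern.** In a two one-sided tests procedure the significance level applies to each one-sided test. At 0.05 per test, both tests reject exactly when the two-sided 90% interval lies inside the margin. Requiring the 95% interval to lie inside the margin is the same procedure at 0.025 per test. Section 6.8 therefore computes power for an easier rule than the one in section 6.10, and the powers it reports do not belong to the planned analysis.

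Two things are at stake. The first is the meaning of the stated sizes, above all the 29 pairs labelled as the minimum, which is the only floor the protocol names should completion fall short. The second is clarity of the primary conclusion. If the 90% interval lay inside ±0.11 and the 95% interval did not, the level in section 6.8 would support equivalence and the rule in section 6.10 would not.

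**Working it through.** **Inputs, all from Protocol sections 6.8 and 6.10:** margin ±0.11; true difference 0; common SD 0.62; correlation 0.95; 29, 36 and 60 pairs; level 0.05 in 6.8; two-sided 95% interval in 6.10.

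**SD of the paired difference:** 0.62 × √(2 × (1 − 0.95)) = 0.62 × √0.10 = 0.1961.

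**Power.** Equivalence is declared when |d̄| + t(1−α, n−1) × s/√n < 0.11, where d̄ is the mean paired difference and s its estimated SD. Power is the probability of that event, integrated over the chi-square distribution of s². A simulation with 400,000 draws agreed to within about 0.2 percentage points.

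**Illustration at 36 pairs, with s set to its true value.** The standard error is 0.1961/√36 = 0.0327, so the margin is 0.11/0.0327 = 3.37 standard errors.
- 90% interval: t = 1.69, leaving 3.37 − 1.69 = 1.68 standard errors of room either side of zero. Power is about 2Φ(1.68) − 1 = 91%.
- 95% interval: t = 2.03, leaving 3.37 − 2.03 = 1.34. Power is about 2Φ(1.34) − 1 = 82%.

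The exact calculation, which allows for the estimated SD, gives slightly lower values:

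| Pairs | Stated in 6.8 | 0.05 per side (90% CI) | 0.025 per side (95% CI, rule in 6.10) | Stated minus 95% rule |
|---|---|---|---|---|
| 29 | 80.7% | 80.7% | 66.1% | 14.6 points |
| 36 | 90.2% | 90.2% | 81.1% | 9.1 points |
| 60 | 99.2% | 99.2% | 97.9% | 1.3 points |
| 20 (one diagnosis) | none stated | 56.1% | 33.9% | – |

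**Smallest sizes.**
- At 0.05 per side: 29 pairs for 80% (28 pairs give 78.8%) and 36 for 90% (35 give 89.2%). These are the protocol's own numbers.
- At 0.025 per side: 36 pairs for 80% (35 give 79.4%) and 44 for 90% (44 give 90.7%, 43 give 89.8%).

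This rules out the reading that 0.05 in section 6.8 was meant as two-sided, with 0.025 on each side. On that reading 36 pairs would have been reported as 81.1%, not 90.2%.

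**Period effect.** The planned model includes period, which costs one degree of freedom. With n − 2 degrees of freedom the 95% rule gives 65.9%, 81.0% and 97.9% at 29, 36 and 60 pairs, so the result does not change.

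**The case against.** The strongest reply is that the trial is not harmed. It plans 60 pairs, where the loss is 1.3 points, and recruitment runs until that target is met. Supplementary Table S1 of the SAP shows 20 enrolled in each diagnosis. Even if 12 of the 60 were lost, 48 pairs would give about 93.5% under the 95% rule. The mismatch also errs on the safe side: the applied rule is stricter, so false declarations of equivalence do not become more likely. No text makes 29 or 36 pairs a stopping or acceptance threshold. The arithmetic in section 6.8 is correct at its own level, so the fault is a mismatch between two sections.

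All of this stands, and it limits the consequence: no change to the sample size, margin or analysis follows. It does not make the stated powers correct. Section 6.8 still calls 29 pairs the minimum for 80% power when the declared rule gives 66.1%, and its size for 90% power is in fact the size for 80%.

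On single diagnoses, the protocol claims no power at 20 pairs and presents those analyses as exploratory. They are weak under either rule (56% or 34%), so the mismatch explains only part of the low figure. Stating it is still useful, because looking within diagnoses is the reason given for enrolling 60, and 99.2% is the only power quoted beside that reason.

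**Conclusion.** The concern holds. Sections 6.8 and 6.10 use different confidence levels, and all three stated powers are too high for the rule that will decide the trial: by 14.6 points at 29 pairs, 9.1 at 36 and 1.3 at 60. If a trial ended with 29 completed pairs, about one in three truly equivalent comparisons would fail (100% − 66.1% = 33.9%). That is conditional, since 60 are planned.

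The figures rest on the protocol's assumptions of SD 0.62, correlation 0.95 and no true difference. The comfort at 60 pairs depends on the correlation. Taking 0.90 purely as an illustration, since the documents do not give that value, power at 60 pairs would be 83.6% under the 90% rule and 71.2% under the 95% rule, and the choice of level would then matter.

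**What to change.** Keep 60 participants and the 95% interval rule. In Protocol section 6.8 and in SAP Section 3, Power and sample size:

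- Describe the calculation as two one-sided tests at 0.025 each, matching the two-sided 95% interval used for the decision.
- Replace the figures with 44 pairs for at least 90% power (90.7%), a minimal size of 36 pairs for at least 80% (81.1%), and 97.9% at 60 pairs. Update the per-diagnosis counts in brackets to match: 36 pairs is 12 per diagnosis, and 44 rounds up to 15 per diagnosis (45 pairs).
- State that 97.9% is for the pooled analysis, and that a single diagnosis with 20 pairs has about 34% power on the same assumptions. A subgroup interval that crosses the margin should then not be read as evidence of a difference.

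The cost is a few sentences and slightly less favourable power figures. No extra participants are needed and the analysis does not change.

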6.9. Randomisation and group allocation

6.9.1. Sequence generation

All participants who fulfil the eligibility criteria and who provides written informed consent for par-

ticipation, will be enrolled and randomly allocated. A computer-generated randomisation sequence

Side **11** af **27**

will be produced before any patients are enrolled, allocating participants in permuted blocks of 2 to

4. The randomisation sequence will be prepared by a senior biostatistician with no clinical involve-

ment in the study ([name] [RC]) and entered into the e-CRF in DANBIO by the independ-

ent data manager NSK. The sequence generation will be prepared with a 1:1 allocation ratio, stratified

by diagnosis (i.e. RA, SpA or PsA). We will use SAS PROC PLAN to generate the 3 mutually inde-

pendent randomisation schedules (3 diagnoses); SAS statistical software (version 9.4.).

6.9.2. Allocation concealment mechanism and implementation

After the participant is enrolled in the study (including signing informed consent), participants will

be randomly allocated to the order of PROM-reporting scheduling modality after the physician

"clicks" on the "randomisation button" in the electronic Case Report Form (e-CRF) in DANBIO (i.e.

according to the sequence generation above). The randomisation number and assigned order will then

be visible on the screen in DANBIO. Thus, the allocation will be concealed from the researcher en-

rolling participants and assessing study related data (LU).

6.9.3. Blinding

The interventions in this study are not blinded.

6.10. Statistical methods

This study is designed and will be carried out as a randomised cross-over agreement study. Thus,

patients will be randomly assigned to one of two groups - completing either data registration on the

smartphone app or the touch screen solution first. The order of questionnaires will be held constant,

but patients enter the sequence at different time points starting with either the "App" or "Touch

screen" version. Thus, each participant will answer the questionnaires through the app and the touch

screen in randomised order at two successive periods (I or II), separated by a "washout period" of

one day. In the cross-over design, each participant acts as his/her own control for questionnaire com-

parisons. This simple manoeuvre is attractive primarily because it increases the statistical power.

Cross-over designs could suffer from a number of problems that can invalidate the results. A potential

caveat related to cross-over studies concerns carryover (i.e. the residual influence of questionnaire

recall in the subsequent period). We will attempt to evaluate and interpret a possible carryover effect

statistically from the interaction between the main effects of questionnaire (app vs. touch screen) and

Side 12 af 27

Clinical Trials number: NCT03486613

time period (I vs. II); realising, however, that the statistical test will lack power because the corresponding contrast is a 'between participant' analysis. We anticipate that a "washout period" of one day will be enough to avoid carryover (i.e. recall) bias. In addition, the arthritis conditions we include in this study are considered chronic and relatively stable, and thus it is highly unlikely that effects of their concomitant medication will interfere with the objective of this study (assessed only a couple of days apart). Another caveat to the clinical interpretation of a cross-over design could be the complications of analysis and interpretation arising from the loss of participants. We expect that losses of participants from the study will be small as the two data registration is done within one day, thus we do not anticipate that this will be an issue. A common, and generally satisfactory, use of the 2×2 cross-over design is to demonstrate the equivalence of two interventions (i.e. questionnaires) all other things being equal. We assume that an equal amount of participants will not adhere to the protocolised data collection ($n_{AT} \approx n_{TA}$).

Data will be analysed using SAS Proc Mixed. The MIXED procedure fits a variety of mixed linear models. A mixed linear model is a generalization of the general linear model (GLM); the generalization being that the data are permitted to exhibit correlation (i.e., from two measures on the same participant). Having a continuous outcome as the dependent variable (e.g. HAQ), our modelling component of SAS PROC MIXED will include both fixed (period [I or II]; questionnaire [App or Touch]; rheumatic condition [RA or PsA or SpA]) and random participant (i: 1, 2, 3,, n = 60) effects. In case of missing data for some of the participants, PROC MIXED handles the missing values implicitly adjusting for the missing values; unlike a GLM approach a mixed linear model uses the data for the periods where there is data and ignores the periods for which there is no data (10). Provided the data are "missing at random", the estimates from PROC MIXED are valid (e.g., the missing data cannot caused by some event happening during the first questionnaire exercise) (11). Imputations will not be used to replace missing data in the primary analyses, but will potentially be included in a sensitivity analysis to assess the impact/robustness of the conclusions.

Statistical interpretation of agreement: According to Piaggio et al. (12), equivalence is declared if the entire 2-sided 95%CI is included within the equivalence margin. Therefore, in this study a 2-sided 95% CI for the paired difference in each individual PROM (e.g HAQ) will be derived from the mixed linear model and agreement will be declared if the 95% CI of difference between PROMs is within the prespecified equivalence range (e.g., -0.11 HAQ-points to +0.11 HAQ-points). These margins (Table 1) are based on half of the effect that is usually considered a clinically relevant reduction in the individual PROMs. Thus, based on a superiority approach it was decided *a priori* that a 95% CI

excluding differences between groups of greater than half the MID/MCID units would be interpreted

as indicating the absence of a clinically meaningful difference (agreement) (13). No interim analyses

will be performed. All reported P values will be two-sided, based on a superiority assumption, and

will not be adjusted for multiple comparisons.

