Statistical analysis plan (SAP) for the DANBIO app agreement trial entitled "Patient-reported outcome measures collected in DANBIO reported via a smartphone app vs a touchscreen solution in an outpatient clinic among patients with inflammatory arthritis: A randomised, crossover, agreement

Trial registration: Clinical Trials number: NCT03486613.

SAP version

Version 1.0

November 7th 2019

Protocol version

This document has been written based on information contained in the study protocol version 1, dated December 21st 2018.

SAP revisions

None

Roles and responsibility

LU and RC designed and wrote this SAP for "the DANBIO app versus touchscreen agreement trial" in accordance to the CONSORT statement for randomised crossover trials (1). LU and RC is responsible for analysis of the trial results according to the SAP.

[name] Student, Principal investigator [name] Professor, Senior Biostatistician, [name], PhD

Section 2: Introduction

Background and rationale

Rheumatoid arthritis (RA), psoriatic arthritis (PsA) and axial spondyloarthritis (axSpA) are three major inflammatory arthritic diseases in Rheumatology. Since the 1980's, patient-reported outcome measures (PROMs) have been used in clinical research and later also in daily clinical practice as an essential tool to evaluate the patient's perception of arthritis activity. Initially, PROMs was collected in a paper form; however, in Denmark, PROMs are more feasibly collected electronically through a touchscreen solution in the outpatient clinic since 2008 (2).

Today, due to the widespread use of smartphones it is now possible and feasible to use the participants' own device for collecting PROM data via a downloaded smartphone app. Using a smartphone app instead of the standard touchscreen solution in the outpatient clinic is anticipated to eliminate problems such as having to wait in a queue, lack of privacy, and uncomfortable position during data entering etc. Furthermore, data can be collected when and where it suits the individual patient best; thereby, possibly providing more accurate answers and minimising recall-bias.

In rheumatology, Health Assessment Questionnaire Disability Index (HAQ-DI) is among the most frequently used PROMs to asses patients with RA, PsA and axSpA (3–5); thus, it makes sense to consider HAQ-DI to be one of the essential PROMs to evaluate patients with these inflammatory arthritis diseases (3–5).

Aims

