Participant enters PROM data through the 1st device	
Washout period	
Participant enters PROM data through the 2 nd device	

Section 4: Statistical Principles

Confidence intervals and P values

Level of statistical significance and use of confidence intervals

All applicable statistical analyses will be 2-sided based on a superiority framework; i.e. all confidence intervals will be presented as 95% and two-sided (95%CI).

Rationale for any adjustment for multiplicity

All applicable statistical tests and 95% confidence intervals presented will be 2-sided. Even in equivalence trials (illustrating comparability), the selection of an appropriate statistical strategy for dealing with multiplicity (repeated statistical tests) is critical for performing reliable inferences and maximizing the probability of a chance finding. Multiplicity considerations play a central role in the assessment of competing clinical objectives; i.e. the more comparisons that are made, the more likely it is that a comparison that appears to be statistically important will be falsely so (i.e. that the PROM devises appear different or with too wide 95%CIs). In order to preserve the family wise error rate of the multiple analyses, the multiplicity of the analyses of the primary and selected secondary PROMs will be presented and interpreted using a gatekeeping procedure (8). The analysis interpretation will be performed in sequence until one of the analyses has failed to be within the prespecified equivalence margin (see Table 2 below).

Adherence and protocol deviations

Acceptable compliance to the protocol is defined as participants who complete both first and second PROM data registration within the scheduled time frame.

Pre-defined major protocol violations that might occur are:

- Not completing the first and second PROM data registration
- Not completing the second PROM data registration
- No wash out period between the first and second data registration i.e. second registration performed on day 2

Pre-defined minor protocol violations are:

Delayed second data registration i.e. PROM data registration with a washout period of > 1
 days i.e. second data registration at day 4 or later

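### The rule declaring agreement PROM by PROM conflicts with the SAP's stop-at-first-failure rule, and that sequence has no named outcomes and no clearly fixed order

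*Protocol*

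**What the plan says.** **Protocol 6.10.** The interval for each individual PROM comes from the mixed model, and "agreement will be declared if the 95% CI of difference between PROMs is within the prespecified equivalence range". No order and no stopping point are given. The same section ends by saying that reported P values are two-sided, rest on a superiority assumption and "will not be adjusted for multiple comparisons".

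**SAP Section 4, rationale for multiplicity adjustment.** The aim is stated first: "In order to preserve the family wise error rate of the multiple analyses". The method is that the primary and "selected secondary PROMs will be presented and interpreted using a gatekeeping procedure". The stop rule follows: "The analysis interpretation will be performed in sequence until one of the analyses has failed to be within the prespecified equivalence margin", with a pointer to Table 2. The false finding to be guarded against is described as "that the PROM devises appear different or with too wide 95%CIs".

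**SAP Section 6, statistical interpretation of agreement.** The protocol's PROM-by-PROM rule is repeated without mention of a sequence.

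**Status of the SAP.** It is dated 7 November 2019 and follows protocol Appendix 8 in the same file. It says of itself: "This document has been written based on information contained in the study protocol version 1". It does not mention that its multiplicity rule departs from protocol 6.10.

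**The concern.** Two rules for the same claim stand in the plan, and the SAP contains both. Under one, every PROM whose interval fits its margin is declared equivalent. Under the other, a PROM can meet its margin and still receive no formal claim because one before it failed. A published list of PROMs for which the app may replace the touchscreen could therefore depend on which section is followed.

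The stop rule is also not fully specified. A fixed sequence controls the family-wise error only if its members and their order are set in advance. Here the selected secondary PROMs are not named, and the order is at best implied by a table.

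Finally, the rationale treats failure to show equivalence as the false finding. In an equivalence test the false positive is declaring two devices equivalent when they are not. A stop rule limits that error. It does nothing to prevent devices from looking different or intervals from being wide.

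**Working it through.** **1. The plan's own figures.** The multiplicity rules carry no number. The nearest stated figures are the HAQ powers in protocol 6.8. Inputs: SD 0.62, correlation 0.95, margin ±0.11, true difference 0, one-sided 0.05 per test.

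- SD of the paired difference = 0.62 × √(2 × (1 − 0.95)) = 0.196.
- Exact paired two one-sided tests power: 90.2% at 36 pairs, 80.7% at 29, 99.2% at 60. All three match the protocol.
- The decision uses a two-sided 95% interval ("equivalence is declared if the entire 2-sided 95%CI is included within the equivalence margin"), so each side is tested at 0.025. HAQ power at 60 pairs is then 97.9%, so the first step is likely to be passed on the plan's assumptions.

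**2. The two rules on the same data.**

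| Outcome | 95% CI inside margin? | PROM-by-PROM rule | Stop rule |
|---|---|---|---|
| HAQ | yes | agreement | agreement |
| VAS pain | no | none | none, stop |
| VAS fatigue | yes | agreement | no formal claim |

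The HAQ row is identical because HAQ is the sole primary outcome and comes first.

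**3. Is an early failure plausible?** The documents give no SD of the difference for the VAS scales, so it is assumed. With 60 pairs, a ±5 mm margin and a true difference of 0, the chance that the 95% CI fits is 93.6%, 77.5% or 55.3% for an SD of the difference of 10, 12 or 14 mm.

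**4. How often would the lists differ?** The lists agree only if all passes come before all failures. For k independent outcomes, each passing with probability p:

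P(differ) = 1 − Σ p^j (1 − p)^(k − j), summed over j = 0 to k.

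For k = 8: 6.8% at p = 0.99, 30.0% at 0.95, 51.6% at 0.90 and 77.6% at 0.80. Both p and independence are assumptions; positive correlation between PROMs would generally lower these figures.

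**5. Family-wise risk of a false equivalence claim.** The eight outcomes are HAQ plus the seven PROMs in protocol 6.7.2 (VAS pain, fatigue and global, PASS, anchoring question, BASDAI, BASFI). With each true difference on its margin, each false claim has probability at most 0.025.

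- PROM-by-PROM rule, independent outcomes: 1 − 0.975^8 = 0.183.
- Fixed sequence: the first outcome whose devices truly differ by the margin or more must be wrongly declared equivalent before any later error can occur, so the risk is at most 0.025.

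**6. Is an order fixed?** Positions in the two tables:

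- Protocol Table 1: HAQ, three VAS scales, BASDAI, BASFI, PASS, anchoring question, DAS28crp, ASDAS.
- SAP Table 2: HAQ-DI, three VAS scales, PASS, anchoring question, DAS28crp, ASDAS, BASDAI, BASFI.

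DAS28crp and ASDAS are not in the list of secondary outcomes, yet in SAP Table 2 they precede two that are. Position matters. BASDAI and BASFI are measured in SpA only, planned at 20 patients. With 20 pairs the half-width of the 95% CI exceeds 5 points once the SD of the difference passes about 10.7, and no result can then meet the margin. Placed before PASS, such a failure would block PASS and the anchoring question; placed last, it would block nothing else.

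**The case against.** Several stronger readings are tempting, and the documents do not support them.

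- **That the sentence on unadjusted comparisons itself contradicts gatekeeping.** Its subject is P values on a superiority assumption. Equivalence is decided by the CI, and a fixed sequence alters neither a P value nor an interval. The sentence can stand beside the stop rule. The conflict lies in the PROM-by-PROM declaration rule.
- **That the main result is at risk.** It is not: HAQ is judged first, on the same interval and margin, under either rule.
- **That the rule could be chosen freely after seeing the data.** The SAP is the later document, makes its authors responsible for analysis according to it, and says no data are analysed before it is final. A SAP may tighten a protocol. This goes far to settle SAP against protocol, but not Section 4 against Section 6 within the SAP.
- **That the sequence is the Table 2 order.** The pointer to Table 2 follows the words on margins and may refer only to them. DAS28crp and ASDAS may already lie outside the sequence. This leaves the order less determined.
- **That the risk is 22%, from ten outcomes (1 − 0.975^10 = 0.224).** That needs all ten independent and at their margins. With joint counts and CRP fixed (protocol 6.7), DAS28crp varies only through patient global at 0.014 per unit (Appendix 7). Its ±0.6 margin corresponds to 0.6 / 0.014 ≈ 43 units, against ±5 mm for VAS global, so the two cannot both sit at their margins in the same patients.
- **That gatekeeping makes devices look different more often.** It only withholds a formal claim. The reversed rationale is a fault of wording that leaves the procedure unchanged, and the same paragraph does state the family-wise aim.

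**Conclusion.** The point holds for the secondary equivalence claims. The PROM-by-PROM rule in protocol 6.10 and SAP Section 6 and the stop rule in SAP Section 4 can give different lists of equivalent PROMs from the same data, and no text says that one replaces the other. The family-wise control announced in the SAP is not secured while the selected outcomes are unnamed and the order is open.

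The difference in risk is about 18% against at most 2.5% for at least one false equivalence claim over eight outcomes. The 18% is an upper-end figure resting on independence and on every true difference lying at its margin. How often the lists would differ depends on pass probabilities that the documents do not give. The primary HAQ conclusion is unaffected.

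**What to change.** Before any analysis:

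1. State in SAP Section 4, and again in the agreement rule of SAP Section 6, that the fixed sequence governs formal equivalence claims and supersedes the PROM-by-PROM rule of protocol 6.10.
2. Name the outcomes and give one order, starting with HAQ-DI and covering the seven listed secondary PROMs. SAP Table 2 without the two composites would serve: HAQ-DI, VAS pain, VAS fatigue, VAS global, PASS, anchoring question, BASDAI, BASFI. Place DAS28crp and ASDAS outside the sequence.
3. Say that outcomes after a failure are reported with their estimates and 95% CIs, descriptively.
4. Rewrite the rationale so that the error controlled is a false declaration of equivalence.
5. Keep the protocol sentence on unadjusted P values if it is limited to the superiority P values.

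The cost is wording only; design, sample size and models are untouched. The downside is that a PROM placed after a failed one loses its formal claim even if its own interval fits the margin.
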